All subjects will complete the demographic form at baseline. The KCCQ (Appendix 2) and Vigor scale from the Profile of Mood States (POMS) will be completed in CTSU visits at baseline and 12 weeks (Appendix 3) along with the subject's height and weight. The patient will be escorted to a private room and asked to remove clothing above the waist. A disposable gown will be provided and the patient will lay supine on the bed while an echocardiogram is completed. Approximately 0.5 ml of blood will be collected via finger stick to measure lactate, ATP, and BNP. Next, the subject will complete a 6MWT (Appendix 4, Borg scale). Approximately 2 hours will be required for each subject's visit to the CTSU. Follow-up calls will occur at 3, 6, and 9 weeks during the trial.

Potential Problem and Alternative Solutions. Serum CoQ10 and D-ribose values in some of the treatment patients might be below threshold levels at 6 weeks, possibly due to subject non-adherence. If this occurs, the Project Director, who is not blinded to the list of placebo and treatment subjects, will call and ask if there are any problems with consuming the ubiquinol and/or D-ribose. The Project Director and Research Associate will conduct a phone follow-up interview at 3, 6, and 9 weeks during the trial using a structured interview. Questions asked will relate to any side effects and compliance history in taking their capsules or powder.

Various cardiovascular risk factors will be recorded such as tobacco usage, diabetes mellitus, hypercholesterolemia, hypertension, and family history of cardiovascular disease. Smoking status will be recorded as either smoker or non-smoker. Patients who use tobacco will be given contact information for a tobacco/smoking cessation program. Diabetes mellitus will be determined by a history of the disease or use of medication for diabetes. Hypercholesterolemia will be defined as a fasting total serum cholesterol level ≥ 4.9 mmol/l or use of medication. Hypertension will be defined as either systolic or diastolic blood pressure $\geq 140/90$ mmHg or use of hypertensive medications.

C.3. Aims and Hypotheses.

AIM #1: *To determine the effects of oral ubiquinol, D-ribose, or a combination of the two administered during 12 weeks on symptoms accompanying low bioenergetics in patients with HFpEF.*

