Hypothesis #1. Ubiquinol (600 mg daily), D-ribose (15 g daily), or a combination of the two will enhance the health status of patients with HFpEF as measured by the Kansas City Cardiomyopathy Questionnaire (KCCQ).

Primary outcomes of the study are patient-centered, thus the measurement of health status will be a priority. Bioenergetics has both biological and behavioral components. The biological component (i.e., improved heart function) and its measurement will be discussed below (Aim #2). In this section we will discuss the behavioral component that relates to patients' perceptions of their health status (i.e., symptoms) and the impact of their health status on daily functioning (e.g., hobbies, work, and energy).

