Using the Vigor subscale from the POMS questionnaire,²⁹⁻³¹ patients will rate themselves on eight adjectives (lively, active, energetic, cheerful, alert, full of pep, carefree, and vigorous) on a five-point scale (0 = not at all, 1 = a little, 2 = moderately, 3 = quite a bit, and 4 = extremely). The Vigor scale has very high internal consistency (Cronbach's alpha = 0.90), and it takes only 1 minute to complete. In many studies it has been found to be effective for assessing vigor changes associated with exercise.³²⁻³⁴ The KCCQ and POMS Vigor scale will be administered to patients after they have been sitting quietly for 10 minutes at the beginning of each visit (baseline and 12 weeks). The total time for patients to complete both questionnaires will be 5 to 10 minutes. We anticipate that during the course of treatment the patients taking these supplements will report increasingly greater improvements in health status, daily functioning, and levels of energy.

Potential Problem and Alternative Solutions. Some older subjects may have difficulty reading the KCCQ or the POMS Vigor scale due to visual problems. We will have copies of both items in LARGE font available for those subjects. If that is not sufficient to solve the problem, we will read each item to the subject and complete the KCCQ and POMS Vigor scale for them if given verbal consent.

AIM #2: *To determine the effects of oral ubiquinol, D-ribose, or a combination of the two over 12 weeks on biological measures in patients with HFpEF.*

Hypothesis #3. Ubiquinol (600 mg daily), D-ribose (15 g daily), or a combination of the two will improve left ventricular diastolic function measured by advanced echocardiographic imaging in patients with HFpEF.

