| Groups and Number of Subjects (69 per group/Total = 276 subjects). The power analyses require 62 subjects/group, but there will be 69 subjects/group based on the expected 10% attrition. | |
| 1. Control Group (Usual Care) N ₁ = 69 subjects: Receive no ubiquinol and no D-ribose; placebo capsules and powder per day. | 2. Ubiquinol Group N ₂ = 69 subjects: Receive 600 mg of ubiquinol per day; D-ribose placebo powder per day. |
| 3. D-ribose Group N ₃ = 69 subjects: Receive 15 g of D-ribose per day; placebo capsules for ubiquinol per day. | 4. Ubiquinol + D-ribose Group N ₄ = 69 subjects: Receive 600 mg ubiquinol and 15 g of D-ribose per day. |

Power and Statistical Analyses. Our power computations described below suggest including 62 subjects in each of the four study groups (ubiquinol, D-ribose, ubiquinol + D-ribose, and placebo). Since we expect about a 10% attrition rate, we will include 69 subjects in each group for a total of 276 subjects who will be randomized to one of the four groups. Efforts will be made to recruit 50% females. As suggested by the reviewers, we will oversample minority populations to increase the generalizability of data for minority groups (30% Black/AA, 30% Hispanic/Latino, 30% White, and 10% Other). In each group there will be Black/AA = 21, Hispanic/Latino = 21, White = 21, American Indian/Alaska Native, Asian, Native Hawaiian/Pacific Islander = 6 (Total = 69). A 10% attrition rate is anticipated since this is the approximate rate [name] (Co-PI) has experienced with her heart failure clinical trials at the same locations. Reasons for the subject's attrition were that they did not want to continue in the study, change in geographic location, or illnesses.

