1.1. Human Subjects Involvement, Characteristics, and Design. The involvement of human subjects in the work outlined in the Research Strategy includes two visits to the Clinical and Translational Scientific Unit (CTSU), obtaining echocardiograms and digital punctures (finger sticks), completing questionnaires, and receiving three follow-up phone calls by research staff. As suggested by the reviewers, we will oversample minority populations to increase the generalizability of data for minority groups (30% African American (AA), 30% Hispanic/Latino, 30% White, and 10% American Indian/Alaska Native, Asian, Native Hawaiian/Pacific Islander). All patients **included** in this study will: be 50 years old or older; have left ventricular ejection fraction (EF) $\geq 50\%$ documented by an echocardiogram within 12 months of enrollment; be diagnosed with HFpEF within a 12-month period; HFpEF, have symptoms of dyspnea and New York Heart Association (NYHA) Classification II or greater symptoms, have a diagnosis of HFpEF defined by one of the following: (1) previous hospitalization for HF with radiographic evidence (pulmonary venous hypertension, vascular congestion, interstitial edema, or pleural effusion) of pulmonary congestion, (2) invasive hemodynamics, (3) echocardiographic evidence of diastolic dysfunction, (4) elevated NT-pro (>400 pg/ml) or BNP (>200 pg/ml), or (5) no use of intermittent sublingual nitroglycerin within 12 months; be 50 years old or older; have left ventricular ejection fraction (EF) $\geq 50\%$ documented by an echocardiogram; are diagnosed with HFpEF within a 6-month period; have willingness to provide informed consent; have a telephone or reliable phone contact; and have their own means of transportation to the study site. Patients will be **excluded** based on any of the following criteria: (1) acute coronary syndrome in the past 12 weeks; (2) significant valvular heart disease; (3) severe cardiac fibrosis (galectin-3 level > 26 ng/ml); (4) constrictive pericardium; (5) pulmonary fibrosis; (6) congenital heart disease; (7) hypertrophic or infiltrative cardiomyopathy; (8) heart transplant; (9) left ventricular assist device; (10) HF associated hospital admission or emergency room visit within past 30 days; (11) recent percutaneous coronary intervention; (12) significant renal and/or hepatic dysfunction; (13) severe cognitive impairment; or (14) consumption of any CoQ10 (ubiquinol) or D-ribose supplements. Hepatic and renal dysfunction will be defined as an ICD-10 code with diagnosis of renal and/or hepatic failure in the patient's healthcare record. For retention we will schedule the sessions at a convenient time for each participant. Two nurse practitioners and a cardiologist on this application who work in the outpatient HF clinics will refer patients to the research team. Also, potential patients with HFpEF who are in the Frontiers participant registry will be contacted, screened, and enrolled in the study. In this randomized, double-blind, placebo-controlled trial, eligible subjects will be randomized to receive either ubiquinol (600 mg daily po), D-ribose (15 g daily po), a

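### The KCCQ and Vigor scale have no remote route at week 12, so a participant who can never return to the clinic has no post-baseline value in any planned analysis

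*Combined protocol and SAP*

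**What the plan says.** C.3 (Hypothesis #1) sets the order of importance: "Primary outcomes of the study are patient-centered, thus the measurement of health status will be a priority". C.2 fixes where and when the two scales are obtained: they "will be completed in CTSU visits at baseline and 12 weeks". C.3 (Hypothesis #2) agrees, placing both at the start of those same two visits after a short rest.

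Between visits, C.2 states: "Follow-up calls will occur at 3, 6, and 9 weeks during the trial". On content it adds: "Questions asked will relate to any side effects and compliance history in taking their capsules or powder". Under Adequacy of Risk Protection the calls are limited to less than 5 minutes. Section 1.1 on human subjects summarises the participant's involvement as two visits with their tests, "completing questionnaires, and receiving three follow-up phone calls by research staff". No telephone, postal or electronic route is given for either scale. C.1 mentions participants' preferences about calls and data collection but sets no such procedure.

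The plan does have retention measures. Visits are timed for when patients feel able to travel (Adequacy of Risk Protection) and are rescheduled if they cannot (2.2, repeated in section 1.3 of the monitoring plan). A bonus is paid for completing both visits (2.1).

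C.5 budgets about 10% attrition, raising 62 per group to 69, and gives the reasons seen in earlier trials: "they did not want to continue in the study, change in geographic location, or illnesses". The Hypothesis #1 and #2 tests are t-tests on change from baseline to week 12. The treatment-duration analysis in C.5 admits a participant who has a change to week 6 or a change to week 12, and adds a joint model for informative drop-out.

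**The concern.** Attendance at week 12 is tied to the symptoms that the KCCQ measures. Section 1.3 on potential risks itself says that visits may be inconvenient, particularly when symptoms are present. If sicker patients fail to return, the KCCQ and Vigor t-tests compare patients well enough to travel. If that happens unevenly across arms, the estimated effect is biased.

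The missing-data models in C.5 look like a safeguard, but they need at least one post-baseline KCCQ, and under the visit schedule the only one is at week 12. Yet the information may be obtainable. Relocation and illness can prevent a clinic visit without preventing a short questionnaire, and having a telephone is a condition of entry.

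**Working it through.** **Step 1. Does any analysis retain a participant with no week-12 visit?**

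| Source | KCCQ at week 6 | KCCQ at week 12 |
|---|---|---|
| C.2 and C.3 (procedures) | not collected | clinic visit only |
| Section 1.1 (two visits, three calls) | no visit; calls carry no scale | clinic visit only |
| C.5, Hypotheses #1 and #2 | not used | required |
| C.5, treatment duration | assumed available | assumed available |

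A participant with no week-12 visit has neither change score. The t-tests cannot include that person. The random-intercept model cannot either, because its entry condition is one of the two changes. C.5 is therefore inconsistent with C.2, C.3 and section 1.1 about week 6.

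**Step 2. Reproduce the plan's figures.** Inputs from C.5: difference 10 points, SD 12.3, n = 62 per group, two-sided alpha 0.05/4 = 0.0125.

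- Effect size: 10/12.3 = 0.813.
- Power: 97.9% by the normal approximation and 97.6% by the noncentral t, against the stated 98% or more. This agrees within rounding.
- Inflation: 62/0.90 = 68.9, so 69. This agrees.
- Expected loss: 69 x 0.10 = 6.9, about 7 per arm; 276 - 4 x 62 = 28 in all.

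**Step 3. Power regained.** Assume that about half of the 7 are reached, giving 65 to 66 evaluable per arm. Noncentral-t power at alpha 0.0125:

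| Evaluable per arm | d = 0.7 | d = 0.813 |
|---|---|---|
| 62 | 91.1% | 97.6% |
| 65 | 92.6% | 98.1% |
| 66 | 93.0% | 98.3% |
| 69 (all recovered, upper bound) | 94.1% | 98.7% |

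The gain is 1.5 to 1.9 points at d = 0.7 and 0.5 to 0.7 points at d = 0.813. It depends on the SD. With an assumed SD of 18, power is 71.1% at 62 and 73.6% to 74.4% at 65 to 66.

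**Step 4. Bias.** Let m be the fraction lost in an arm and D the amount by which KCCQ change is worse in those lost than in those seen. The full-arm mean is (1 - m) x C + m x (C - D) = C - mD, where C is the completers' mean. Completers overstate the arm mean by mD. With the same D in both arms, the between-arm bias is (m1 - m2) x D in absolute value. The documents give neither D nor a split of loss by arm, so both are assumed.

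| Loss in the two arms | D = 5 | D = 10 | D = 15 |
|---|---|---|---|
| 15% and 5% | 0.5 | 1.0 | 1.5 |
| 10% and 10% | 0 | 0 | 0 |

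For scale, the target difference is 10 points, and the standard error of a two-group difference at 62 per arm is 12.3 x sqrt(2/62) = 2.2 points.

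**Step 5. Can the scales be given by telephone?** C.3 puts the KCCQ at 4 to 6 minutes, Vigor at 1 minute and the pair at 5 to 10 minutes. For participants with visual problems it already permits staff help: "we will read each item to the subject and complete the KCCQ and POMS Vigor scale for them". The existing calls do not fit as they stand: none is at week 12, and each is capped at under 5 minutes. A separate call would be needed.

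**The case against.** The strongest reply is that the plan already handles most of this. A reader might infer that everyone who misses week 12 is lost; the documents do not support that, because visits are rescheduled around inability to travel and completion is rewarded. What remains is the participant who can never return. No week-12 window is stated, so how far rescheduling stretches is unclear.

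A reader might also infer that two-thirds of attrition is recoverable, since two of the three listed reasons concern travel. C.5 gives no frequencies, and the first reason is unwillingness to continue, which may extend to a call. The sickest may also be hard to reach. The half recovered is an assumption, and 7 per arm is an upper bound.

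The loss is budgeted in the move from 62 to 69, so this is not a sample-size fault. The bias scenario is hypothetical, vanishes under equal loss and gap, and at its largest (1.5 points) is smaller than the standard error. These objections stand, and they set the priority.

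Reading items aloud is a last resort within a visit, for a scale the plan describes as self-administered. Telephone scores would come only from non-attenders, so mode and non-attendance are confounded. That also stands, and limits what a sensitivity analysis can show.

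The C.5 missing-data models do not answer the point. Even if a week-6 KCCQ were added, it would help those models but would not supply the week-12 change that the t-tests need.

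**Conclusion.** The point holds in limited form. A participant who cannot attend week 12 at all contributes no post-baseline KCCQ or Vigor score to the t-tests or the random-effects models. The concern is possible informative missingness in the priority outcome. The documents do not show that the trial would be underpowered or that its result would be biased.

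Power rises by at most about 3 points at d = 0.7 and about 1 point at d = 0.813 even if all 7 per arm are recovered. The bias of 0.5 to 1.5 points rests on the assumed unequal loss and the assumed gap. A remote fallback is a cheap, optional improvement to an acceptable design. The firmer defect is the week-6 KCCQ that C.5 assumes and no procedure collects.

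**What to change.** 1. In C.2 and section 1.1 on human subjects, add that when the week-12 visit is missed and cannot be rescheduled, a staff member blinded to allocation makes a separate week-12 call of about 5 to 10 minutes to complete the KCCQ and Vigor scale with any randomized participant who agrees. This should not be the Project Director, whom C.2 describes as unblinded.
2. In C.5, include these scores in the Hypothesis #1 and #2 analyses, record the mode of completion, and report results with and without telephone scores. State that this is a comparison with the attenders-only analysis and does not isolate a mode effect.
3. Reconcile the treatment-duration analysis in C.5 with C.2, C.3 and section 1.1: either the schedule collects a week-6 KCCQ, or the model and its missing-data claim are rewritten for the data that will exist.

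Cost: at most about 28 calls by existing staff, plus a protocol and consent line. Downsides: telephone and self-completed scores may differ, and some who withdraw will also decline the call.

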1.0 Participants Safety

1.1. Potential Risks and Benefits for Participants

Ubiquinol has been found to have an acceptable safety profile as a dietary supplement with multiple daily doses. The potential risk to study participants for ubiquinol includes mild gastrointestinal symptoms at high doses around 1000 mg/day. For D-ribose oral administration of D-ribose up to 15 g/kg/d is safe. Minor side effects include diarrhea, gastrointestinal discomfort, and slight nausea. Subjects may experience minimal pain/discomfort from digital puncture, possible bruising and swelling around the puncture site, especially for subjects who are taking anticoagulant therapy; uncommonly faintness is associated with the procedure. Although the potential risks for subjects participating in the 6-minute walk test (6MWT) may be changes in blood pressure, heart rate, and lightheadedness, it is often well tolerated and without reported complications.

The potential benefits to study participants include improved energy level, increased overall health status (reduced physical limitations, less symptoms of heart failure with preserved ejection fraction (HFpEF), increased self-efficacy, expanded social interactions, and improved quality of life), and enhanced cardiac performance.

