Exercise-based testing is essential in evaluating the functional capacity and response to therapy and prognosis of patients with HF.⁵⁵ The 6-minute walking test (6MWT) is a simple clinical tool which has been shown to be linearly related to oxygen uptake.⁵⁶ The ease and cost of the 6MWT gives it advantages compared to other tests.⁵⁷ Mortality and morbidity in chronic HF have been predicted with the 6MWT. It was found that patients with a walking distance of less than 300 meters (325 yards) had 50% mortality at 1 year; the mortality of those walking more than 450 meters was less at 1 year. In addition, there was an inverse relationship between distance walked and hospitalization rates.⁵⁸

We will examine the effects of ubiquinol and/or D-ribose on the 6MWT at baseline and 12 weeks. Participants will be asked to wear appropriate clothes and shoes and walk the longest distance possible in 6 minutes. Prior to exercising, there will be a 10-minute rest period during which heart rate and blood pressure will be recorded. Subjects will walk indoors on a flat, straight 30-meter path marked every 3 meters, and they will be informed that they can slow down or stop at any time. A one-lap demonstration will be completed before the test begins. The distance walked will be recorded. Following the 6MWT, a 0.02 ml blood sample will be obtained for lactate measurement. Lactate provides a measure of the oxygen debt occurring during exercise and correlates directly with reported dyspnea and fatigue. The patient will also record perceived dyspnea and fatigue at baseline and at the end of each walk by using the Borg scale, where 0 = nothing at all, 5 = severe, and 10 = very severe. Words of encouragement will be offered during the walk and water provided afterward.

Hypothesis #5. Ubiquinol (600 mg daily), D-ribose (15 g daily), or a combination of the two will decrease venous blood B-type natriuretic peptide (BNP) levels in patients with HFpEF.

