1.3. Potential Risks. No appreciable risk of physical, psychological, financial, legal, or other harm to the study subjects is expected. Ubiquinol is naturally produced in the human body, and the safety of high doses of orally-ingested CoQ10 for long periods is well established.⁹⁰⁻⁹² Specifically with ubiquinol, Hosoe et al. found that it was safe, tolerable, and bioavailable at various oral dosages. They also found effectiveness of oral ubiquinol in just 4 weeks.⁹¹ No serious adverse events were observed and no significant safety concern was raised. Thus, ubiquinol was found to have an acceptable safety profile as a dietary supplement with multiple daily doses. Only mild gastrointestinal symptoms have been reported in a small number of subjects; these were not dose-related and occurred in both ubiquinol and placebo groups.⁹¹ D-ribose is a simple sugar that is also naturally produced in the human body and used for energy production. Extended toxicity studies have shown that oral administration of D-ribose up to 15 g/kg/d is safe. Only minor side effects were reported, including diarrhea, gastrointestinal discomfort, and nausea.⁹³⁻⁹⁵ The time and efforts required for two visits to the CTSU may be an inconvenience to patients with HFpEF, especially when they are experiencing symptoms. Subjects may experience minimal pain/discomfort from digital puncture, or possible bruising and swelling around the puncture site, especially for subjects who are taking anticoagulant therapy; uncommonly, faintness is associated with the procedure. Although the potential risks for subjects participating in the 6-minute walk test (6MWT) may be changes in blood pressure, heart rate, and lightheadedness, it is often well tolerated and without reported complications.⁹⁶

2. Adequacy of Risk Protection.

The CTSU visits will be scheduled at a convenient time when patients with HFpEF feel comfortable to travel. The follow-up telephone calls made by the Project Director or Research Associate will include structured questions that are brief (less than 5 minutes), between the hours of 9 a.m. and 6 p.m. (or other times if specified by the subject), and are neutral in voice and tone.

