3.2. Content of Data and Safety Monitoring Report

The content of the data and safety monitoring report will include: study status, participant descriptive information, safety information, and study quality. Prior to subject recruitment, the members of the DSMB will read the written study protocols, informed consent procedures, Data Safety Monitoring (DSM) policies, and plan.¹⁰⁰ Members of the DSMB will initially discuss the plan for clarification of their responsibilities, the board structure, and organization and rules of operation, as noted in the policies. All trial progress and DSMB advice on continuation, modification, or termination are reported to the Principal Investigator ([name]), IRB, and the NIA Program Officer.

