- Administering ubiquinone in some studies resulted in poor gastrointestinal absorption. In addition, the ability to convert ubiquinone to ubiquinol (active form) was decreased.¹¹⁶⁻¹¹⁹ This conversion is not an issue for individuals in the 20-40 year age range^{120, 121} but it becomes increasingly difficult for individuals older than the age of 40.^{122, 123}
- With the use of ubiquinol, there is no impairment of absorption in patients of any age. With the introduction of ubiquinol the efficacy has greatly increased in many diseases^{105, 124, 125} including congestive heart failure.^{126, 127}

D-ribose

Safety

- D-ribose is safe and well tolerated in the daily doses smaller than 20 grams.¹²⁸⁻¹³⁰ In this study, subjects will be consuming 15 grams/day. Subjects may experience loose stools. This effect can be

circumvented by avoiding D-ribose ingestion on an empty stomach or by taking three 5 gram doses at various times of the day.

- For the study, we will use Dual Health 100% Pure D-Ribose Powder. It is a pharmaceutical USP Grade D-Ribose that is a white to slightly yellow crystalline powder, characterized by a fruity sweet odor and slightly sweet taste.
- The Dual Health D-ribose is produced in the USA and from a CGMP manufacturer and has a certificate of analysis for the product.
- The D-ribose from Dual Health is United States Pharmacopeia (USP) and Food Chemical Codex (FCC) graded and is 100% pure without fillers or additives. Thus, it is a certified dietary supplement that through testing and evaluations is a safe product for human consumption.
- D-ribose readily dissolves in water, juice, milk, and other cold liquids and has been determined to be safe with few adverse side effects.¹³¹
- D-ribose may lower blood pressures ¹³²

Efficacy

- Impairment of adenosine triphosphate (ATP) synthesis results in energy demand exceeding energy supply, which results in depletion of ATP accompanied by diastolic dysfunction. Research has shown that supplementing exogenous D-ribose accelerated synthesis of ATP by six-fold.¹³³
- Increased ATP levels by D-ribose improved cardiac energy metabolism and contributed to significant recovery of myocardial contractility.^{134,135}
- D-ribose significantly improved diastolic function and patients' exercise tolerance, which enhanced patients' quality of life.⁷¹

Combined Regimen of Ubiquinol and D-ribose

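### Appendix 9 says D-ribose may lower blood pressure, but the two risk sections name only gastrointestinal effects for it, and no planned analysis or named safety summary uses the resting blood pressure already recorded

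*Combined protocol and SAP*

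**What the plan says.** Appendix 9, under D-ribose safety, has one line on blood pressure: "D-ribose may lower blood pressures". It gives no size, rate, dose or population.

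Two sections describe the risks of the supplements. Section 1.3, Potential Risks, in the human-subjects part says of D-ribose: "Only minor side effects were reported, including diarrhea, gastrointestinal discomfort, and nausea". DSMP 1.1 says: "Minor side effects include diarrhea, gastrointestinal discomfort, and slight nausea". Both also mention blood pressure, but only for the walk test. DSMP 1.1 puts it this way: "the potential risks for subjects participating in the 6-minute walk test (6MWT) may be changes in blood pressure, heart rate, and lightheadedness".

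Blood pressure is measured. Under Hypothesis #4 in C.3: "Prior to exercising, there will be a 10-minute rest period during which heart rate and blood pressure will be recorded". The walk test is done at baseline and at 12 weeks.

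For monitoring, DSMP 3.2 says: "The content of the data and safety monitoring report will include: study status, participant descriptive information, safety information, and study quality". Between visits there are phone interviews at weeks 3, 6 and 9, of which C.2 says: "Questions asked will relate to any side effects and compliance history in taking their capsules or powder".

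**The concern.** The plan names a possible effect of one of its products in an appendix and then leaves it out of the two sections that staff and the DSMB would consult for risks. Those sections do offer other explanations for related symptoms: lightheadedness appears under the walk test and faintness under the finger stick. A reader of those pages alone has a procedural reason for such symptoms and no D-ribose reason.

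The plan also collects the readings that could show whether resting pressure falls on D-ribose, but asks nobody to compare them. DSMP 1.2 collects adverse occurrences as subjects report them, so a fall in pressure without recognised symptoms need not surface at all.

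Some participants may be on blood-pressure-lowering treatment. The definition of hypertension in C.2 allows for "or use of hypertensive medications", and C.3 notes that guideline treatment for this condition includes several such drug classes. The share of participants taking them is not given. The exclusion criteria in C.1 contain no low-blood-pressure criterion.

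**Working it through.** **Text check.** The places where blood pressure could appear, side by side:

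| Place | What it has on blood pressure |
|---|---|
| Appendix 9, D-ribose safety | Possible lowering by D-ribose |
| Section 1.3, Potential Risks | Walk-test risk only |
| DSMP 1.1 | Walk-test risk only |
| C.2, recorded risk factors | Part of the definition of hypertension |
| C.3, Hypothesis #4 | Recorded at rest before the walk, baseline and week 12 |
| C.5, all analyses | None. The outcomes are KCCQ and subscales, Vigor, E/e', PAP and other diastolic indicators, walk distance, BNP and lactate/ATP |
| DSMP 1.2 | No blood-pressure threshold. Collection is by subject report |
| DSMP 3.2 | Safety information in general; vital signs neither named nor excluded |

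The effect is therefore named once, the measurement is planned, and no comparison links the two.

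**Would the comparison be informative?**

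Inputs from C.5: 62 evaluable per group, 10% attrition, 69 randomized per group, four groups. The plan's own inflation reproduces: 62 / 0.90 = 68.9, rounded up to 69.

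- Assigned to D-ribose: 2 × 69 = 138, and 138 / 276 = 50%.
- Completers on each side of D-ribose versus no D-ribose: 2 × 62 = 124.
- Expected without a week-12 reading: 138 − 124 = 14 per side.

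The 95% confidence half-width for the difference in mean change is t(0.975, 246 df) × √(2/124) × SD = 1.970 × 0.1270 × SD = 0.250 SD.

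The documents give no SD for blood-pressure change, so it has to be assumed:

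| Assumed SD of change (mmHg) | Half-width (mmHg) |
|---|---|
| 12 | 0.250 × 12 = 3.0 |
| 15 | 0.250 × 15 = 3.8 |
| 18 | 0.250 × 18 = 4.5 |

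Pooling across ubiquinol keeps the two sides balanced on it, but the pooled difference is an average over ubiquinol use. It is easy to interpret only if ubiquinol does not change the effect of D-ribose on blood pressure. The figures show how precise the table would be. They say nothing about the size of any effect.

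**The case against.** The strongest reply is that the information is already in the plan and the safeguards are already adequate.

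- **The risk lists are open.** Both are worded as examples, so they do not deny a blood-pressure effect. This stands, although an open list is still better for including an effect that the same document names.
- **The DSMB can see Appendix 9.** C.2 refers to that appendix, and DSMP 3.2 has members read the written protocol and consent procedures before recruitment. This stands too. The gap is one of cross-reference, and the DSMB is not deprived of the information.
- **Serious events are well covered.** Under DSMP 1.2 all serious adverse events go to the DSMB and NIA, and DSMP 3.1 sets 2 business days for this. DSMB members are available in real time. The cardiologist who makes the final determinations is unblinded and can weigh D-ribose assignment for each reported event. Sections 2.2 and DSMP 1.3 ask for immediate reporting of side effects and give a route to the cardiologists. All of this stands.
- **The table is a blunt instrument.** Two resting readings 12 weeks apart, with no timing relative to dose, say little about brief or individual falls. A completer-only mean leaves out anyone who stopped because of hypotension. This is correct, and it is why the table needs a count of missing readings beside it.

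A reader might infer that participants are not warned of a known risk. The documents do not support that. The consent form is not available here, DSMP 1.3 says that risks are listed there, and the call script is not reproduced, so it may already ask about dizziness or fainting. A reader might also infer that the trial carries a real risk of hypotensive harm. The single Appendix 9 line does not carry that weight.

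**Conclusion.** The point holds as a minor safety-consistency improvement. Three things are established from the text: Appendix 9 names possible blood-pressure lowering by D-ribose; section 1.3 and DSMP 1.1 name only gastrointestinal effects for it; and no analysis or named safety summary uses the resting readings.

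Half the trial is assigned to D-ribose for 12 weeks, and the comparison could be made to within about 0.25 SD at no measurement cost. The mmHg values rest wholly on the assumed SDs, and the count of 124 per side assumes the planned 10% attrition.

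This is not evidence of harm, and it is not a failure of serious-event oversight. What it would add is the ability to report on an effect that the plan itself names, including falls in pressure that nobody reports as a symptom.

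**What to change.** 1. In the closed DSMB report and the final safety report, give the change in resting blood pressure from baseline to week 12, D-ribose versus no D-ribose, with a 95% confidence interval. Beside it, show by assignment how many participants lack a week-12 reading and why they stopped. Keep the table out of the open sessions, where DSMP 3.5 has data presented blinded.
2. Add possible blood-pressure lowering to the D-ribose risks in section 1.3 and DSMP 1.1.
3. In DSMP 1.2, state that serious related hypotension or syncope still goes directly to the IRB. The current rule sends an event there only if, among other conditions, it was not expected. Step 2 could make hypotension expected and so end that direct report. The DSMB chair's reports would still reach the IRB, and the 2-business-day notice to the DSMB and NIA is unaffected.

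Optional: if the call script does not already do so, ask about dizziness, fainting and falls at weeks 3, 6 and 9. That makes up to 276 × 3 = 828 scheduled calls slightly longer.

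The cost is one descriptive table and a few sentences. There is no new visit or measurement, and no change to eligibility, sample size or any efficacy analysis.
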